emotionally") aspects of transportation. Responses will be provided on a seven-point Likert scale with anchors "very much" and "not at all." This scale is widely used and has demonstrated reliability ($\alpha > .70$) in previous experiments using video games¹⁴⁷ and diverse samples of adult women viewing cancer-related narratives.¹⁴⁸ Only participants in the narrative game group will complete this scale, as its questions do not make sense in the absence of a storyline.

We will pilot test use of the Presence Self-Assessment Manikin as a crude indicator of immersion applicable to both applications. This measure consists of a row of five pictures corresponding to a nine-point Likert scale and has demonstrated predictive validity in a previous study of narrative video games.¹⁴⁹ The pictures show a figure at various distances from a TV screen. Respondents are told that "the pictures go from a person who feels he or she is inside the picture, a part of the story, a part of the action on the left end, to a person who feels he or she is outside the picture, removed or separated from the story, not part of the action on the right end."

The Exercise Imagery Questionnaire is a widely-used measure that includes three subscales: appearance ("I imagine a leaner-me from exercising"), techniques ("When I think about exercising, I imagine my form and body position"), and energy ("To get me energized, I imagine exercising").¹⁵⁰ An additional subscale related to enjoyment ("When I think about exercise, I imagine myself having fun while exercising") will be included.¹⁵¹ The resulting scale has 12 items and responses range from 1 ("Never") to 9 ("Always"). Cronbach's alphas ranged between 0.79 and 0.93 for the four subscales¹⁵¹. Tests of predictive validity have found relationships in the expected directions; for example, appearance imagery predicted controlled motivation, whereas enjoyment and technique imagery predicted autonomous motivation¹⁵¹.

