Character identification cannot be accurately compared across groups, as the monitoring app does not include characters. To provide a proxy for character identification, we will use the procedure described by Przybylski and colleagues for investigating discrepancy between the ideal self and self while playing the game/using the app.⁶¹ Participants will complete the Ten Item Personality Inventory with reference to their ideal self (at baseline), then regarding themselves while using the app (other time points). Correlations between ideal self and game-self for each of the items will be averaged, with neuroticism items reverse-coded, to create a number between -1 and 1 that indicates ideal-self and walking-self convergence. This convergence will be considered a proxy measure of the extent to which identification with the player character led to "trying on" of her characteristics.

The Play Experience Scale is a 16-item scale made up of four subscales: freedom ("I was able to make the game do what I wanted it to"), no extrinsic ("I was not worried about someone judging how I performed in the game"), play-direct ("I would characterize my experience with the game as playing"), and autotelic-focus ("When I was using the game, I was focused on the task at hand"). Responses range from 1 ("Strongly disagree") to 6 ("Strongly agree"). This is a relatively new scale with few published studies using it, but it has demonstrated reliability ($\alpha > .80$) and convergent validity with intrinsic motivation ($r = .79$).¹⁵²

The Basic Psychological Needs in Exercise Scale will measure autonomy ("I feel that the way I exercise is the way I want to"), competence ("I feel that exercise is an activity which I do very well"), and relatedness ("My relationships with the people I exercise with are very friendly"). Responses to this 11-item scale use a 1 – 5 Likert scale ("I don't agree at all" to "I completely agree"). Reported alphas for the subscales were 0.75 or higher.¹⁵³ This scale has been used similarly in past studies, for example to investigate the relationship between perceived competence and exercise role identity (partial $r = 0.20$).¹⁴²

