Basic psychological needs	I feel I have made a lot of progress in relation to the goal I want to achieve The way I exercise is in agreement with my choices and interests I feel I perform successfully the activities of my exercise program My relationships with the people I exercise with are very friendly I feel that the way I exercise is the way I want to I feel exercise is an activity which I do very well I feel I have excellent communication with the people I exercise with I feel that the way I exercise is a true expression of who I am I am able to meet the requirement of my exercise program My relationships with the people I exercise with are close I feel that I have the opportunity to make choices with regard to the way I exercise

[figure not shown]
The nature of narrative transportation scales renders comparisons across groups difficult. Thus, we have included several different scales to measure different aspects of the construct. For measurement within the enhanced group, we will use the Transportation Scale,¹⁴⁶ which is widely used in the literature, and the Narrative Engagement Scale,¹⁶⁴ which provides subscales that may point to interesting areas for future work (narrative understanding, attentional focus, narrative presence, and emotional engagement). To compare the two groups, it was necessary to use a more general measure of presence (also known as engagement or immersion). Table 6.10 shows the items from the two narrative-related scales. Below the table, we have included a self-assessment manikin that is commonly used for brief but valid investigations of a general sense of engagement during a mediated experience (using an app, watching TV, playing a game, etc.).¹⁶⁵

Table 6.10. Questionnaire items related to Narrative Transportation

Transportation Scale	While I was playing the game, I could easily picture the events in it taking place.
	While I was playing the game, activity going on in the room/space around me was on my mind.
	I could picture myself in the scene of the events described in the game.
	I was mentally involved in the game while playing it.
	After finishing the game, I found it easy to put it out of my mind.
	I wanted to learn how the game ended.
	The game affected me emotionally.
	I found myself thinking of ways the game could have turned out differently.
	I found my mind wandering while playing the game.
	The events in this game are relevant to my everyday life.
	The events of the game have changed my life.

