	While playing the game I had a vivid image of my character.
	At points, I had a hard time making sense of what was going on in the game.
	My understanding of the characters is unclear.
Narrative Engagement Scale	I had a hard time recognizing the thread of the story.
	I found my mind wandering while using the game.
	While using the game I found myself thinking about other things.
	I had a hard time keeping my mind on the game.
	While using the game, my body was in the room, but my mind was inside the world created by the story.
	The game created a new world, and then that world suddenly disappeared when the game ended.
	At times during the game, the story world was closer to me than the real world.
	The story affected me emotionally.
	During the game, when a main character succeeded, I felt happy, and when they suffered in some way, I felt sad
	I felt sorry for some of the characters in the game.

Below is the presence Self Assessment Manikin, with the instructions provided to participants:

Please use the figures below to indicate your feelings or emotional response to the game. The pictures go from a person who feels he or she is INSIDE THE PICTURE, A PART OF THE STORY, A PART OF THE ACTION on the left end, to a person who feels he or she is OUTSIDE THE PICTURE, REMOVED OR SEPARATED FROM THE STORY, NOT PART OF THE ACTION on the right end. Please circle the number for the picture, or the space between any two pictures, that best represents how you felt while using the app.

Counseling content example

Below, we present an example from our weekly brief counseling guides. The content and structure of the guides was taken from previous studies performed by co-mentor [name]. The themes for each week reflect standard behavior change counseling content and techniques, such as stimulus control, problem-solving, goal-setting, etc.

Week 3. Uncovering Barriers

[Discuss exercise progress report abstracted from application – ask for totals from the feedback screen(s)]

Last session we discussed finding times to fit in exercise. You mentioned that you wanted to try fitting in exercise _____ . Did you try it? Did you develop plans for the rest of the week? (YES NO) Were you able to fit in exercise in times that you hadn't before? What were they? _____

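### The one immersion measure designated for comparing the arms is worded around a game and a story that the standard arm does not have, so an arm difference on it cannot be interpreted

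*Combined protocol and SAP*

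**What the plan says.** Section F.6 (Other variables) gives the Transportation Scale to one arm and explains why: "Only participants in the narrative game group will complete this scale, as its questions do not make sense in the absence of a storyline". For a measure that spans both arms it turns to the Manikin: "We will pilot test use of the Presence Self-Assessment Manikin as a crude indicator of immersion applicable to both applications". Section G (Questionnaire content) confirms the role: "To compare the two groups, it was necessary to use a more general measure of presence". It then shows the Manikin below Table 6.10.

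Section G also prints the instructions that participants receive. They open with "Please use the figures below to indicate your feelings or emotional response to the game". The high-immersion end is "INSIDE THE PICTURE, A PART OF THE STORY, A PART OF THE ACTION on the left end" and the low-immersion end is "OUTSIDE THE PICTURE, REMOVED OR SEPARATED FROM THE STORY, NOT PART OF THE ACTION on the right end". Section F.6 describes the same anchors. The last sentence of the instructions is different: it asks for the picture that best fits how the participant felt when using the app.

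Section F.5 says that Runkeeper was chosen for the standard arm because it has the usual self-regulatory tools and no game or narrative components. No separate Manikin wording for that arm is given.

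**The concern.** The plan withholds one scale from the standard arm because its items assume a storyline. It then compares the arms on another scale whose stem names a game and whose two anchors are both defined by a story. The reason given for withholding the first scale applies equally to the stem and anchors of the second.

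The direction of the problem is predictable. For a woman using Runkeeper, being removed from the story is literally true whatever her engagement with the app. A literal reading moves standard-arm scores only, and towards the result that the trial hypothesises. Randomization does not remove this, and neither does the assessor blinded to group, because the bias lies in a self-reported item.

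At stake is the account of mechanism. Aim 3 includes narrative transportation among the predictors to be investigated. Section F.8 says that other variables follow the same analysis as the primary outcome, so a between-arm test of the Manikin is to be expected. A wording effect could then be reported as support for the conceptual model and carried into the follow-up application described in section F.11.

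**Working it through.** The documents give no figure for the Manikin, so there is nothing to reproduce. The point rests on setting the texts side by side.

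| Element | Text | Meaningful without a game or story? |
|---|---|---|
| Intended use (F.6, G) | both apps; comparison of the groups | – |
| Stem (G) | response to the game | no |
| High anchor (F.6, G) | part of the story and the action | no |
| Low anchor (F.6, G) | removed from the story and the action | literally true by default |
| Closing sentence (G) | feelings when using the app | yes |
| Standard-arm app (F.5) | no game or narrative components | – |

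Only the closing sentence is neutral between the arms. It says what to rate, but the ends of the scale on which the rating is placed still refer to a story.

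**Illustration of how much a shift could matter.** All Manikin inputs here are assumptions.

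- n per arm: 120 × (1 − 0.20) / 2 = 48, from the N and the attrition rate in section F.7.
- True engagement equal in both arms; two-sided 5% test.
- Chance of a significant result ≈ Φ(δ/SE − 1.96), with SE = SD × √(2/48).

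For δ = 1 point and SD = 2: SE = 2 × 0.204 = 0.408, δ/SE = 2.449, and Φ(0.489) = 0.69. Across a range:

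| Wording shift | SD 1.5 | SD 2.0 | SD 2.5 |
|---|---|---|---|
| 0.5 point | 37% | 23% | 16% |
| 1 point | 90% | 69% | 50% |

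**The same question by share of literal responders.** Suppose scores have mean 5 and SD 2 in both arms, and a fraction f of the standard arm answers at the outside end, coded 9. The mean shift is f × (9 − 5) = 4f. The standard-arm variance becomes 4(1 − f) + 16f(1 − f).

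- f = 0.10: shift 0.4; variance 5.04; SE = √((4 + 5.04)/48) = 0.434; chance of significance about 15%.
- f = 0.25: shift 1.0; variance 6; SE = √(10/48) = 0.456; about 59%.
- f = 0.50: shift 2.0; variance 6; SE = 0.456; about 99%.

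A simulation with scores rounded and held within 1 to 9 (4,000 replicates) gave 15%, 60% and 99%. These figures show how sensitive the comparison would be to a given amount of literal answering. They do not show how much literal answering there was.

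**The case against.** Four points can be made for the plan.

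First, the closing sentence asks about the app, so a standard-arm participant has a sensible thing to rate. This stands as far as it goes. A reader might infer that she can only choose the outside end. The documents do not support that, because the instructions are mixed. The neutral sentence reduces the bias without removing it.

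Second, section G describes the Manikin as capturing engagement during a mediated experience. A monitor user who feels outside that experience may be giving a valid low score, and absorption in the walk itself is a different construct. This stands too. It means that the wording cannot be shown to account for all of an arm difference. Equally, a real difference cannot be told apart from the wording effect.

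Third, the plan is candid: it calls the Manikin a crude indicator under pilot test, and section G concedes that comparing the groups on narrative scales is difficult. Neither remark identifies the wording problem, and section G still names the Manikin for the comparison.

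Fourth, little depends on it. The primary endpoint is accelerometer minutes at 6 months, Aim 3's headline comparison is autonomous motivation, and section F.11 leaves formal mediation testing to a larger trial. This limits the consequence to the interpretation of mechanism.

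A reader might also count the Play Experience Scale as a second faulty immersion measure. All four of its example items name the game, for instance "I would characterize my experience with the game as playing", and section F.6 states no restriction by arm. But it measures play, the plan never designates it for comparing immersion, and its use in both arms would have to be inferred from silence. It calls for the same caution only if both arms completed it.

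**Conclusion.** The point holds for the Manikin. It is the plan's one designated cross-arm measure of immersion, and its stem and both anchors presuppose content that the standard-arm app lacks. A between-arm difference is therefore confounded with the wording, in the direction of lower apparent immersion in the standard arm. That conclusion rests on the text alone.

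The size is unknown. It would be tempting to read the shifts of 0.4, 1.0 and 2.0 points, or their false-positive rates, as estimates of the bias in this trial. They are not: the mean, the SD, the equal true engagement, the share of literal responders and their placement at the extreme are all assumed. Nor do the documents show that the wording by itself must produce a difference. The primary endpoint and the sample size are unaffected.

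**What to change.** For data collected with this wording, add a sentence to section F.8: the Manikin will be reported descriptively by arm, or within the enhanced arm only, and a between-arm difference will not be interpreted as evidence that the narrative game is more immersive. Apply the same caution to the Play Experience Scale if both arms completed it.

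Do not switch wording within this study. The COVID-19 text in section F.4 says that enrolment is complete, so a change now would mix two versions among participants. In any new cohort or follow-up trial, use one wording that refers to the app, with anchors that need no story, in both arms from the start.

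The cost is that the between-arm comparison of immersion is lost or carries a caveat. For future use, reworded scales depart from the cited versions. For the Manikin this means replacing the verbal anchors of a pictorial scale, so the cited evidence of validity would not transfer automatically.
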